3.2.2 Primary Endpoint

The primary safety and effectiveness endpoint is 2 Year Composite Clinical Success requiring the following:

- An improvement in the Adjusted Constant Score (for pain, function and range of motion) from baseline (pre-op) to the Month 24 time-point that is ≥ 10 points and a final Adjusted Constant Score ≥ 54 .

- Radiographic success at the Month 24 time-point which is defined as absence of clinically significant humeral radiolucency, humeral migration/subsidence (relative to 3 month time point), glenoid radiolucency, glenoid migration/subsidence (relative to 3 month time point), device disassembly or fracture, and/or periprosthetic fracture, as described in the radiographic protocol
- No reoperation, removal, or modification of any study component up to the subject's completion of the study.
- No serious device-related complications up to the subject's completion of the study.

For a patient to be considered a success, he or she must meet all of the above criteria.

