3.2.3 Secondary Endpoints

The following will be evaluated as secondary endpoints:

- Adjusted Constant scores and radiographic success evaluated at each time point.
- The percentage of patients achieving an Adjusted Constant Score ≥ 70 at each time point.
- SF-36
- VAS

4 Study Population: Inclusion and Exclusion Criteria

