Grade 4: Complete radiolucency (> 2 mm wide) around 2 or more pegs

Grade 5: Gross loosening

Success Criterion for Glenoid Radiolucency: Grade ≤ 3 glenoid Radiolucency

- **Rationale:** Previously, researchers have utilized a glenoid lucency of ≥ 4 (per criteria of Lazarus 2002) to determine those patients “at risk” for device malfunction due to glenoid lucency as 24 Months post-op. Haines et al. (2006) observed, in a prospective clinical trial of shoulder arthroplasties (n=124 shoulders, n=113 patients), 14% of patients at > 24 Months had a glenoid lucency score ≥ 4 (per criteria of Lazarus 2002). These patients, having what the authors describe as “at risk” implants, demonstrated a 78% survival rate at seven years, but only a 46% survival rate at ten years, compared to a survival rate of 84% at 10 years for the entire patient cohort. (Haines et al. 2006)

Glenoid Migration/Subsidence

Glenoid Migration/Subsidence will be graded as ‘Absent’ or ‘Present’

- **Absent:** Glenoid component displacement ≤ 3 mm relative to the baseline time point
- **Present:** Glenoid component displacement > 3 mm relative to the baseline time point

Glenoid Migration/Subsidence Endpoints will be assessed for change relative to month 3 image.

Success Criterion for Glenoid Migration: Absent Glenoid Migration/Subsidence**Device Condition**

Device Condition will be evaluated to assess the condition and integrity of the device. Device Condition will be graded as ‘Intact’, ‘Disassembly’ or ‘Fracture’ in accordance with the following definitions:

- **Intact:** No evidence of fractured or disassembled hardware. The hardware is intact.
- **Disassembly:** Presence of device component disassembly
- **Fracture:** Presence of fracture or breakage of one or more device components

Success Criterion for Device Condition: Intact device condition**Periprosthetic Fracture**

Periprosthetic fracture will be graded as ‘Absent’, ‘Present – Humeral’ in accordance with the following definitions:

- **Absent:** No evidence of periprosthetic fracture(s) about the humeral or glenoid components

- **Present – Humeral:** Presence of periprosthetic fracture(s) about the humeral component that is not present on the relative baseline time point

Success Criterion for Periprosthetic Fracture: Absence of device-related Periprosthetic fracture

4. No reoperation, removal, or modification of any study component up to the subject's completion of the study

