10.8 Treatment of Missing Data

As previously described, patient success will be defined at Month 24 postoperatively on the basis of a Composite Clinical Success (CCS) criterion. If the Month 24 CCS endpoint is missing due to a clinical evaluation (i.e., Constant score or radiographic results) unavailable at the Month 24 interval but available at a later date (i.e., after the end of the Month 24 interval), the later clinical evaluations will be used to impute missing values. The roll-back imputation is typically considered conservative since in most orthopedic study, maximum recovery is achieved earlier than 24 Months.

It is expected that there will be at least a few patients with missing Month 24 CCS despite the use of Month 24+ roll-back for clinical and radiographic components of the Month 24 CCS. A tipping point analysis will be performed in order to assess the impact of missing data on primary non-inferiority comparisons. Sequentially, at each stage of the tipping point analysis, one missing Month 24 CCS in the investigational device group will be considered as a failure while at the same time one missing value in the control group will be considered a success. Tipping point stages will be sequentially assessed until there are no more missing CCS values in either group.

If the percentage of missing CCS is more than small, e.g., >10%, then the primary sensitivity analysis will involve multiple imputation (Rubin DB, 1991) (MI) rather than tipping point analysis.

MI minimizes the effects of selection bias on the estimates of the proportions achieving Month 24 CCS. A logistic regression method for monotone missing data using SAS procedure Proc.MI (SAS Institute INC, 2006) will be employed to produce multiply imputed outcome determinations for patients missing Month 24 CCS. This method first fits a

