3.3 Qualitative Radiographic Assessments

The following qualitative, visual assessments will be performed by trained, independent radiologists at Medical Metrics:

1. Humeral Radiolucency
2. Humeral Migration/Subsidence
3. Device Condition
4. Periprosthetic Fracture
5. Glenoid Radiolucency (Keeled)
6. Glenoid Radiolucency (Pegged)
7. Glenoid Migration/Subsidence
8. Additional Radiographic Observations

The qualitative assessments will be conducted for both the investigational and control groups at the time points indicated in Table 2 below.

Table 2: Schedule of the Qualitative Assessments

Assessment	Component	Time Points
Humeral Radiolucency	Humeral	3M, 6M, 12M, 24M, AV [†]
Humeral Migration/Subsidence	Humeral	6M, 12M, 24M, AV [†]
Device Condition	Humeral & Glenoid	PostOp, 3M, 6M, 12M, 24M, AV [†]
Periprosthetic Fracture	Humeral	PostOp, 3M, 6M, 12M, 24M, AV [†]
Glenoid Radiolucency (Keeled)	Glenoid	3M, 6M, 12M, 24M, AV [†]

Glenoid Radiolucency (Pegged)	Glenoid	3M, 6M, 12M, 24M, AV [†]
Glenoid Migration/Subsidence	Glenoid	6M, 12M, 24M, AV [†]
Additional Observations	Humeral & Glenoid	PostOp, 3M, 6M, 12M, 24M, AV [†]

[†] Additional and unscheduled visit imaging will be evaluated if collected.

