APPENDIX 1: RADIOGRAPHIC ASSESSMENT SUMMARY

Qualitative Assessments	Evaluations/Comparisons
1. Humeral Radiolucency	
 • Humeral Radiolucency will be evaluated in each treatment group beginning with the 3 Month time point. • Humeral Radiolucency in the Investigational group will be evaluated in 9 zones separately and the Control group will consist of 15 zones evaluated separately.
2. Humeral Migration/Subsidence	
 • Humeral Migration/Subsidence will be evaluated in each treatment group beginning with Month 6 relative to the Month 3 time point. • Humeral Migration/Subsidence will be graded as 'Absent' or 'Present'.
3. Device Condition	
 • Device Condition will be evaluated at each post-operative visit beginning with the PostOp time point. • Device Condition will be graded as 'Intact', 'Disassembly', or 'Fracture'
4. Periprosthetic Fracture	
 • Periprosthetic Fracture will be evaluated in each treatment group beginning with the PostOp time point. • Periprosthetic Fracture will be graded as 'Absent' or 'Present'.
5. Glenoid Radiolucency (Keeled)	
 • Glenoid Radiolucency (Keeled) will be evaluated in each treatment group beginning with the 3 Month time point. • Glenoid Radiolucency (Keeled) will be graded as 'Grade 1 to Grade 5' or 'N/A'.
6. Glenoid Radiolucency (Pegged)	
 • Glenoid Radiolucency (Pegged) will be evaluated in each treatment group beginning with the 3 Month time point. • Glenoid Radiolucency (Pegged) will be graded as 'Grade 1 to Grade 5' or 'N/A'.
7. Glenoid Migration/Subsidence	
 • Glenoid Migration/Subsidence will be evaluated in each treatment group beginning with Month 6 relative to the Month 3 time point. • Glenoid Migration/Subsidence will be graded as 'Absent', or 'Present'
8. Additional Radiographic Observations	
 • Additional observations will be documented at the discretion of the radiologist at all post-operative time points.

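### A radiographic failure already graded before Month 24 becomes a missing CCS when no Month 24 or later film exists

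*Combined protocol and SAP*

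**What the plan says.** The radiographic component of the primary endpoint (section 3.2.2) is tied to a single visit: "Radiographic success at the Month 24 time-point which is defined as absence of clinically significant humeral radiolucency", followed by migration, glenoid lucency, device condition and periprosthetic fracture. The two event components are cumulative: "No reoperation, removal, or modification of any study component up to the subject's completion of the study" and "No serious device-related complications up to the subject's completion of the study".

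The core lab reads much more than the Month 24 film. In Table 2 of the radiographic protocol (section 3.3), device condition and periprosthetic fracture are scheduled at "PostOp, 3M, 6M, 12M, 24M, AV", lucency from Month 3 and migration from Month 6. Appendix 1 of that protocol repeats this: "Device Condition will be evaluated at each post-operative visit beginning with the PostOp time point". The earlier grades are used in a descriptive secondary endpoint: "Adjusted Constant scores and radiographic success evaluated at each time point" (section 3.2.3).

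For a Month 24 evaluation that is missing but available afterwards, section 10.8 says "the later clinical evaluations will be used to impute missing values". It has no rule that uses an earlier film. CCS values still missing go to a tipping-point analysis. If more than about 10% are missing, multiple imputation becomes the primary sensitivity analysis instead; its covariates are not named.

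Section 6.6 and the last note to the Schedule of Events require the full closing visit, radiographs included, from patients who stop early. Neither says how that film enters the CCS.

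**The concern.** Take a patient graded at Month 12 with Grade 4 or 5 glenoid lucency, or with more than 3 mm of migration, who has no reoperation and no serious device-related complication, and who never has another film. The core lab has recorded a failure on the plan's own criterion. Section 10.8 nevertheless treats the outcome as unknown, because it searches only after Month 24.

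In a non-inferiority comparison this loses observed failures from the count. If such patients were more frequent in the Eclipse arm, the difference would look smaller than the recorded gradings show. If they were more frequent among controls, the error would run against Eclipse. Either way the primary result would rest on fewer failures than the core lab has on file.

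**Working it through.** **What happens to the patient under the rules**

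1. Month 24 film: none, so the radiographic component cannot be judged as section 3.2.2 defines it.
2. Later film: none, so the section 10.8 roll-back does not apply.
3. Earlier failed film: no rule in 3.2.2, in the CCS criteria (item 3) or in 10.8 carries it forward.
4. Event components: not triggered unless there was a reoperation or a serious device-related complication.
5. Result: missing CCS. Section 10.8 handles it only by tipping point or multiple imputation, so it is either absent from the primary comparison or imputed.

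**The plan's own figure**

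Inputs from section 10.4: 88% success in both arms, margin 0.10, one-sided alpha 0.05, 196 Eclipse and 98 control. Power = Phi(0.10/SE - 1.645).

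- SE = sqrt(0.88 x 0.12/196 + 0.88 x 0.12/98) = 0.0402
- Power = Phi(2.487 - 1.645) = 80.0%, as stated.

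**Illustration of size**

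The documents give no rate of such patients, so the numbers added are assumptions. Start from 88% of each arm, rounded: 172/196 and 86/98. Lower limit = pE - pC - 1.645 x sqrt[pE(1 - pE)/nE + pC(1 - pC)/nC], with pC = 0.8776.

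| Eclipse failures added | Eclipse | pE | Difference | SE | Lower limit |
|---|---|---|---|---|---|
| 0 | 172/196 | 0.8776 | 0.000 | 0.0406 | -0.067 |
| 6 | 172/202 | 0.8515 | -0.026 | 0.0415 | -0.094 |
| 8 | 172/204 | 0.8431 | -0.034 | 0.0418 | -0.103 |

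Eight patients are 8/204 = 3.9% of that Eclipse group. If the arms are affected equally, 172/204 v 86/102, the difference is 0, the SE is sqrt(0.1323/204 + 0.1323/102) = 0.0441, and the limit is -0.073. The conclusion changes only with an excess in the Eclipse arm.

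**Cost of counting them**

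Suppose success falls to 87% in both arms, with 196/98 held: SE = sqrt(0.87 x 0.13/196 + 0.87 x 0.13/98) = 0.0416, and power = Phi(2.403 - 1.645) = 77.6%.

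**Is the 10% switch within reach?**

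Section 10.4 inflates 294 to 347, so 53/347 = 15.3% are allowed for loss and exclusions together, and the plan expects exclusions for eligibility violations to be few. Missing CCS above 10% is therefore within what the plan provides for.

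**The case against.** The strongest reply is that the tipping-point analysis already covers this. It turns missing Eclipse values into failures and missing control values into successes, one pair at a time, until none remain. At its last stage it is at least as hard on Eclipse as the proposed rule. With 8 Eclipse and no control values missing, it gives the same 172/204 v 86/98 and -0.103, and 8/302 = 2.6% missing is below the switch to imputation. This is correct, and the plan would show the problem in that case. But it would be a sensitivity result beside a primary result that omits the failures. It treats a known failure like an unknown outcome and would score a control with a known failed film as a success. It also gives way to imputation when missingness is greatest.

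Second, patients who stop early should have a closing film, so the gap mainly concerns those lost without a closing visit. The Schedule of Events puts Month 24 and End of Study in one column, which may mean that the closing film is to stand in for Month 24. If so, the plan should say so; it does not.

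Third, a reader might infer that an early disassembly, device fracture or loosening can be scored a success on a clean Month 24 film, and that failure on any film should therefore count. The documents give little support for this. Earlier failures that are reoperated, or are serious device-related complications, already fail the CCS. Migration is measured against the Month 3 film, so Month 24 captures cumulative displacement. An unrevised mechanical failure would normally still be visible. What remains is mainly a healed fracture or a grade that reverses on a later reading. Assessment at Month 24 is stated consistently. An any-film rule would also clash with the fracture definition in section 10, which requires "Presence of periprosthetic fracture(s) about the humeral component that is not present on the relative baseline time point" and limits failure to device-related fracture.

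**Conclusion.** The gap is real and narrow. Section 10.8 as written leaves an observed radiographic failure out of the failure count when no Month 24 or later film exists, and no other rule restores it. It deserves correction because the grading already exists, but it does not invalidate the endpoint.

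Its size cannot be known from the documents. On the planned numbers with equal observed success, 8 such patients, all in the Eclipse arm, would move the limit past the margin; 6 would not, and equal proportions in both arms would not.

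A reader might infer that the type I error of the primary test is inflated. The documents do not support that. It would need an excess in the Eclipse arm that no document reports, and it would take the truth to be at the margin on a different endpoint, failure at any visit. For the Month 24 endpoint as defined, no inflation has been shown.

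**What to change.** Add to section 10.8: if no Month 24 or later film exists, and the last gradable core-lab film (scheduled, unscheduled or early-termination) failed any radiographic success criterion of CCS item 3, the CCS is a failure and not missing. Keep the existing limits on periprosthetic fracture, namely new since the baseline film and device-related. State that a reading graded Indeterminate or Unable to Assess is not gradable for this purpose. Apply the rule identically in both arms.

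Leave the Month 24 definition in section 3.2.2 unchanged. Failure on any earlier film can be a pre-specified sensitivity analysis.

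The change needs no new data, but under section 8.16 an amendment needs FDA and IRB approval. The statistical cost is slightly lower success rates and power: about 77.6% at 196/98 if both arms fall to 87%.

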3.2.3 Secondary Endpoints

The following will be evaluated as secondary endpoints:

- Adjusted Constant scores and radiographic success evaluated at each time point.
- The percentage of patients achieving an Adjusted Constant Score ≥ 70 at each time point.
- SF-36
- VAS

4 Study Population: Inclusion and Exclusion Criteria

4.1 Study Population

4.1.1 Intention to Treat (ITT) Cohort

The investigator will invite prospective patients to enroll in the study that meet the inclusion/exclusion criteria and have signed the informed consent. All patients randomized to either the investigational device (ArthroX Eclipse™ Shoulder Prosthesis) or the control device (ArthroX Univers™ II Shoulder Prosthesis) will be included in the ITT cohort. Randomization will take place after patients have been screened for inclusion and exclusion criteria. Patients found prior to randomization to not meet all inclusion and exclusion criteria will be defined as screen failures and will not receive the investigational device. These patients will be excluded from the ITT cohort.

4.1.2 Per Protocol (Efficacy Evaluable) Cohort

Patients included in the ITT cohort but found to have been randomized in error will be excluded from the Per Protocol (Efficacy Evaluable) cohort. A patient will be considered to have been randomized in error if it is determined that the patient has clinically significant violations of the inclusion or exclusion criteria. Because approval and labeling is sought for patients meeting study inclusion and exclusion criteria, primary non-inferiority testing will be conducted in the Per Protocol (Efficacy Evaluable) cohort. Safety endpoints will be summarized for the Per Protocol cohort for the same reason. However, all adverse events that occur in the study will be reported in safety listings based on the ITT cohort.

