24. The subject has osteoporosis defined as a bone density T score of ≤ -2.5 . (A screening Questionnaire for osteoporosis, SCORE (Simple Calculated Osteoporosis Risk Estimation) and MORES (Male Osteoporosis Risk Estimation Score), will be used to screen patients who require a DEXA bone mineral density measurement.

Timeline:	Initial Enrollment:	10/2012
	Last Enrollment:	12/2017
	Last Subject Visit	7/2019
	Last Close-out Visit	10/2019
Study Duration:	
The length of the Study will be 24 months post-operative*.
 
V 1 Screening : -21 days to day 0
 
V2 Surgery: day 0
 
V3 Post-op: 3 months =90 days +/- 14 days
 
V4 Post-op: 6 months = 180 days +/- 30 days
 
V5 Post-op: 12 months =360 days +/- 60 days
 
V6 Post-op: 24 months = 720 days +/- 60days
 
* If the study is prematurely terminated the investigator will promptly inform active subjects to ensure adequate follow-up for the subjects according to their standard of care practices.
	
Monitoring:	
ArthroX Clinical Research [name] [name] Ph.: [contact]
	

2 Introduction

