6.1.3 Enrollment Status

Screening Status:

Subject's that have signed the informed consent and have data collected at Visit 1 will be considered Screened.

Randomized:

Only those patients who meet the inclusion and exclusion criteria.

Treated:

Once implanted the subject status will update to either Implanted - Eclipse or Implanted - Univers II.

Screen Failed:

Screen failures are those subjects who have signed the informed consent and data has been collected at visit 1, but are not eligible or not able to start treatment. Subjects that were screened and randomized but had to have a non study total shoulder replacement will be consider a Screen Fail.

Once the subject is determined to be a "Screen Fail" and the End of Study form is completed (with the reason) in the EDC, the subject status will update to Screen Fail. An enrollment log of all subjects screened for the study. The reason(s) for screen failure will be recorded on the log.

Early Termination:

Subjects that are screened, randomized, and implanted with the Univers II or the Eclipse but drop out prior to 24 months (720 days +/- 60days) will be considered Early Termination.

Potential reasons for "Early Termination" may include, but are not limited to:

- Subject participation in a clinical trial is voluntary. The subject may discontinue participation (refuse all subsequent testing and follow-up procedures) at any time without penalty or loss of benefits.
- The investigator may terminate the subject's participation without regard to the subject's consent if the investigator believes it is medically necessary and in the best interest of the subject.
- Lost to Follow-up: The subject does not complete the 24 month follow-up but has not "officially" withdrawn from the study.
 - Failure to return for follow-up visits is not a criterion for withdrawal.
 - In order to consider a subject lost to follow-up, site personnel should make all reasonable efforts to locate and establish communication with the study subject. All attempts should be

documented within the source documents, indicating date, time, method, and site personnel.

- A minimum of three documented attempts should be made without response from the study subject in order to classify a subject as lost to follow-up.

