10.4 Sample Size Analysis for Primary Non-Inferiority Test

Given the above criteria, the Sponsor expects a success rate of 88% for both the Eclipse and control group.

To determine the required sample size, it was assumed that the above primary hypotheses will be tested using 1-sided $\alpha=0.05$ at a statistical power of at least 80%. Under these assumptions, nQuery Advisor 7.0 module PTE0U-1 produces the following:

“When the sample sizes in the groups are 98 and 196, a two-group large-sample normal approximation test of proportions with a one-sided 0.05 significance level will have 80% power to reject the null hypothesis that the test and the standard are not equivalent (the difference in proportions, $p_T - p_S$, is -0.10 or farther from zero in the same direction) in favor of the alternative hypothesis that the proportions in the two groups are equivalent, assuming that the expected difference in proportions is 0.00 and the proportion in the standard group is 0.88.

Therefore, the total number of Per Protocol (Efficacy Evaluable) patients required under these assumptions are $N=294$. The number of protocol violations of inclusion / exclusion criteria (i.e., randomized in error) is expected to be small. The randomized sample size is adjusted up by 15% to account for both loss-to-follow-up and exclusions due to protocol violation to $N=347$.

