logistic regression model for the outcome variable based on covariates using complete cases. Then, based on the fitted regression model, a new logistic regression model is simulated from the posterior predictive distribution of the parameters which is then used to impute the missing outcome variables. This is done by using the model to compute the expected probability of clinical success for each patient missing the outcome. A uniform random number from 0 to the patient specific expected probability is then generated and if the value is less than the expected probability, the outcome is imputed as a success, otherwise impute the outcome as failure. After all missing outcomes are imputed, the estimated proportion and its standard error will be determined in the usual way. This process will be repeated 20 times. The final point estimate will be determined as the mean value over these 20 multiple imputations. The final standard error used to construct the 95% confidence interval needed for the primary non-inferiority test will be determined from the pooled variance (within imputation variance) plus a term reflecting variability among the 20 multiply imputed point estimates (between imputation variance) (Rubin DB, 1986). The final estimate and 95% confidence interval will be computed by the SAS procedure Proc.MIANALYZE using this approach. By imputing the missing values among patients with missing Month 24 CCS, bias is reduced since the inference is to the entire population that includes patients both missing and not missing Month 24 CCS. The standard error of the final estimate accounts for the statistical uncertainty present in the imputed outcomes and so confidence intervals tend to have the correct coverage rates.

11 Bibliography

Blackwelder, W. (1982). Proving the null hypothesis. *Controlled Clinical Trials*, 3:345-353.

Bohsali KI, W. M. (2006). Complications of total shoulder arthroplasty. *J Bone Joint Surg* , 88, 2279-2292

Boileau, P., et al., *Cemented polyethylene versus uncemented metal-backed glenoid components in total shoulder arthroplasty: a prospective, double-blind, randomized study*. *J Shoulder Elbow Surg*, 2002. **11**(4): p. 351-9.

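### Sections 4.1.2, 10.4 and 10.8 do not settle how a Month 24 composite success still missing after roll-back enters the primary non-inferiority test

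*Combined protocol and SAP*

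**What the plan says.** Four statements bear on this.

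- Section 4.1.2 sets the analysis population: "primary non-inferiority testing will be conducted in the Per Protocol (Efficacy Evaluable) cohort". The only exclusion is: "Patients included in the ITT cohort but found to have been randomized in error will be excluded from the Per Protocol (Efficacy Evaluable) cohort". Section 6.1.3 treats loss to follow-up ("The subject does not complete the 24 month follow-up") as a form of early termination after implantation. Nothing there removes such a patient from the cohort.
- Section 10.4 uses the same cohort name for its 294 patients, then adds 15% for loss to follow-up and eligibility exclusions together, reaching 347 randomised.
- Section 10.8 first rolls back a Constant score or radiograph obtained after the Month 24 interval. This feeds the endpoint itself. For what is still missing it plans a tipping point analysis of the effect on the primary comparison. If more than about 10% is missing, "then the primary sensitivity analysis will involve multiple imputation" in place of the tipping point.
- Later in 10.8 the MI standard error is said to build the confidence interval needed for the primary test. MI is recommended there because "bias is reduced since the inference is to the entire population that includes patients both missing and not missing Month 24 CCS".

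**The concern.** Month 24 composite clinical success (CCS) carries the trial's single primary decision. A patient who is in the cohort but has no CCS must be counted somehow, and no sentence says how. The tipping point text assumes that a primary result already exists without these patients, and the 294 in 10.4 counts only patients with an outcome. Both point to an observed-case test. The last part of 10.8 points to MI instead. Two statisticians could follow the plan and report different primary results.

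The choice matters in a non-inferiority trial. If patients who are doing badly leave more often, completers look better than the randomised group, and more so in the arm with more failures. That can narrow a true deficit even when the rule for leaving is the same in both arms.

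**Working it through.** 1. The plan's own figure. Inputs from 10.4: 88% success in both arms, margin 0.10, one-sided 0.05, 80% power, 2:1. Control n = (1.645 + 0.842)² × (0.88×0.12/2 + 0.88×0.12) / 0.10² = 6.18 × 0.1584 / 0.01 = 97.9, so 98, with 196 Eclipse and 294 in all. Dividing by 0.85: 98/0.85 = 115.3, so 116; 196/0.85 = 230.6, so 231; total 347. Both figures reproduce. So 294 is what remains after loss is taken out, whereas under 4.1.2 the cohort is 347 less the eligibility errors alone, which 10.4 expects to be few.

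2. Same data, different rules. Assumed data: 172/196 v 86/98 observed (87.8% each), with 35 and 18 missing. Lower bound = difference − 1.645 × √(p₁(1−p₁)/n₁ + p₂(1−p₂)/n₂).

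| Rule for the missing | Eclipse | Control | Lower bound (points) | Margin −10 |
|---|---|---|---|---|
| Left out | 172/196 | 86/98 | −6.7 | met |
| All failures | 172/231 | 86/116 | −7.9 | met |
| MI draw as worded (all successes) | 207/231 | 104/116 | −5.75 | met |
| Tipping stage 6 | 172/202 | 92/104 | −9.9 | met |
| Tipping stage 7 | 172/203 | 93/105 | −10.4 | not met |
| Eclipse failures, control successes | 172/231 | 104/116 | −21.8 | not met |

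3. Size of the observed-case bias. The documents give no dropout pattern, so these inputs are assumptions. True CCS is 78% v 88% (the null boundary), with 231 v 116 randomised. Month 12 failure is 25% v 12%, and 40% of those succeed at Month 24. Loss is 30% of Month 12 failures and 10% of the others, in both arms.
   - Success among the others: (0.78 − 0.25×0.40)/0.75 = 0.907; (0.88 − 0.12×0.40)/0.88 = 0.945.
   - Missing: 0.25×0.30 + 0.75×0.10 = 15.0%; 0.12×0.30 + 0.88×0.10 = 12.4%; overall (231×0.150 + 116×0.124)/347 = 14.1%.
   - Observed success: (0.25×0.70×0.40 + 0.75×0.90×0.907)/0.85 = 80.2%; (0.12×0.70×0.40 + 0.88×0.90×0.945)/0.876 = 89.3%. The difference is −9.1 points, not −10.0.

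   Simulated one-sided type I error (unpooled Wald test, nominal 5%; complete data give 4.4%):

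| Loss pattern | Observed-case | Using Month 12 status |
|---|---|---|
| Same in both arms, 14% missing | about 7% | about 4.5% |
| Same in both arms, 9.4% missing | about 6% | about 4.5% |
| Outcome-related in Eclipse only | about 12% | about 4.5% |
| Random | no difference | no difference |

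   Section 3.1 allows control randomisation to halt after 77. If those are evaluable controls, 77/0.85 = 90.6, so 91 are randomised. The first and third observed-case figures become about 6% and 10% to 11%.

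4. Other patterns, with success among the missing set directly (assumed, 231 v 116). At 15% missing in both arms, type I error is 10.1% for 60% v 80% success among the missing, 30.7% for 50% v 88%, but 1.3% for 50% v 50%. With 5% Eclipse and 15% control missing at 50% v 50%, it is 0.06%.

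5. The MI draw in 10.8. A uniform number is drawn between 0 and the patient's probability p, and success is imputed if it falls below p. It always does. In the first scenario of step 3 the rates become 0.682 + 0.150 = 83.2% and 0.782 + 0.124 = 90.6%. The difference shrinks to −7.4 points and type I error rises to about 16%.

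**The case against.** A reader might infer that the plan fixes an observed-case primary test, handles missing CCS only in sensitivity analyses, and so favours Eclipse. The documents do not support that. Roll-back acts on the endpoint and is not labelled a sensitivity analysis. The closing text of 10.8 links the MI interval to the primary test, so MI is not clearly kept out of it. No sentence states an observed-case rule. The direction of bias depends on who leaves, as step 4 shows, and nothing in the documents suggests that loss would depend on outcome in one arm only.

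There are also real safeguards. A reoperation or serious device-related complication before leaving already makes CCS a failure under 3.2.2. Section 6.6 and the Schedule of Events notes ask for end-of-study procedures at early termination. The tipping point sequence is severe. At low missing fractions the effect is small: with the same mechanism in both arms, type I error is 5.6% at 7.1% missing and 5.1% at 4.7%. The label on the 294 could be loose wording only.

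All of this narrows the point without closing it. Roll-back cannot help patients who never return, and the plan does not say whether early-exit measurements count as Month 24 values. Given the 15% allowance and few expected eligibility errors, more than 10% missing is plausible. In that range the tipping point gives way to MI, whose draw is wrong as worded. If the software draws correctly, the text still has to match it.

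**Conclusion.** The point holds as a gap and a contradiction: 4.1.2, 10.4 and the two parts of 10.8 do not yield one primary rule for a CCS still missing after roll-back. Read as observed-case, the test is valid only if loss is unrelated to outcome within each arm. Its type I error would be about 6% to 7% when the same outcome-related loss acts in both arms at roughly 10% to 14% missing, and about 12% if it acts in Eclipse alone. These sizes rest on assumed dropout and Month 12 rates. They vanish under random loss and reverse under some other patterns. Using MI exactly as worded would make matters worse (about 16%). The plan should be corrected before the primary analysis, but nothing here shows that the trial's result is biased.

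**What to change.** In 4.1.2 and 10.8, state one primary rule:

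- The test includes every Per Protocol patient as 4.1.2 defines the cohort.
- A patient already a failure through reoperation or a serious device-related event is counted as a failure.
- Any other CCS still missing after roll-back is multiply imputed within arm, at any missing fraction, from baseline and Month 3, 6 and 12 Adjusted Constant Score and core-lab results.
- The draw is Uniform(0,1), with success imputed if it is below p.

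Keep the observed-case and tipping point analyses as sensitivity analyses at any missing fraction. In 10.4, describe the 294 as patients with an observed CCS. Remove the conflict in 10.8 over whether MI is primary or sensitivity.

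The cost is wording and some programming; the inputs are already collected. Power is somewhat lower where loss is outcome-related: with equal devices and 12% Month 12 failure in both arms (assumed), about 82% to 84%, depending on how Month 12 status is used, against 87% for observed-case.
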